This is a mixed-method study comprising a multi-site Randomised Controlled Trial (RCT) with an internal pilot. The study will also include an economic evaluation, integrated into the RCT design, and a Process Evaluation. The main trial will involve testing Culturally-adapted Family Intervention (CaFI) in four geographical locations (seven NHS Trusts plus two contingency Trusts) across England. This will be done with a Caribbean sample, among whom feasibility and acceptability have been established

Greater Manchester
Mental Health
NHS Foundation Trust

(HS&DR Feasibility Pilot) (Edge et al., 2016) and people of Sub-Saharan African origin and their families (including those who self-identify as 'Black British' and 'Mixed' heritage) in inpatient, rehabilitation, community and forensic settings.

Study setting

The study will take place in psychiatric hospitals, community and forensic settings in seven NHS Mental Health Trusts across England and two contingency sites. To facilitate recruitment, we have focused on Trusts in urban areas with high proportions of the target population. Greater Manchester Mental Health NHS Foundation Trust will be the host organisation. Reflecting CQC reported variation in service provision, 5 participating Trusts (including the contingency sites) are rated 'good' overall whilst 4 'require improvement' (Care Quality Commission, 2017). Undertaking the trial across a number of geographically dispersed organisations provides the opportunity to identify, compare and address potential barriers to implementation and share good practice in terms of uptake and embedding psychological care.

Sample size

An existing meta-analysis indicates a relative risk of 0.55 for relapse after family intervention without cultural adaptation (Pharoah et al., 2006); 40% of controls relapsed. A reduction in risk of relapse from 40% during follow-up to 24% (i.e. a risk ratio of 0.6) would equate to a clinically-significant difference sufficiently convincing to inform commissioning and facilitate change in practice. We expect 2% of participants to withdraw consent for rating relapse from case notes (Rabiee & Smith, 2014).

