Using Stata's 'power logrank' command with Schoenfeld's formula, 171 participants per arm would be required for 90% power to detect a hazard ration of 0.6. However, the design of this study, with therapy offered in the intervention arm only, results in a partially nested data structure. We anticipate little therapist effect, but to allow for variation we recalculated the sample size using 'clsampsi' in Stata with an ICC of 0.01 in the intervention arm. With an average cluster size of 11, 198 participants would be required in each arm for 90% power to detect a difference in relapse of 40% in the control arm and 24% in the intervention arm. Inflating for the expected 2% drop out, we require a total sample size of 404. Based on this sample size, we will need to recruit 17 participants per month across all NHS Trusts (see

.

[figure not shown]

Figure 1. CONSORT diagram of the CaFI RCT procedures.

Participants and recruitment procedures

As recruitment will be within communities previously labelled 'hard-to-reach', we shall adopt engagement and recruitment strategies informed by our PPI work and previous HS&DR (CaFI) study. These may include but are not limited to using local media, working with Faith-Based Organisations (FBOs), voluntary sector agencies and community groups.

Within services, we shall place advertisement posters and flyers in participating sites accessible to service users, carers and advocates. We anticipate that the study will be adopted onto the NIHR portfolio. Accordingly, NIHR Clinical Research Network (CRN) Clinical Studies Officers (CSOs) will support recruitment, helping to identify and recruit suitable participants. CSOs and RAs will work collaboratively to publicise the study and inform clinical staff about the inclusion criteria. Recruitment packs, including the study Participant Information Sheet (PIS), will be provided for service users who are deemed well enough to participate by their clinical teams, who have the capacity to consent and who gave permission to be contacted by the research team. Service users who remain interested will be invited to meet with the RA to receive further information about the study and ask any questions before being consented into the study. Consenting participants will be asked to complete baseline assessments during the initial meeting. An additional meeting will be arranged if this is not feasible.

Target population

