Control arm - Treatment as usual

Service users in both treatment and control groups will receive usual care. This usually involves medication with support from nurses. Lack of FI generally (Fadden, 1997) and specifically for Black people (National Collaborating Centre for Mental Health, 2008) were confirmed by our feasibility trial (Edge et al., 2016). We also know that some of our proposed sites do not have resources for psychological interventions in psychoses so usual care is not psychologically based. Accordingly, we do not anticipate that participants will concurrently be offered structured FI or similar psychological intervention although this is subject to potential changes in commissioning. We shall make structured FI an exclusion criterion but allow informal family support or FI occurring more than 6 months previously and record FI as part of usual care post-randomisation.

Assignment of interventions

Randomisation will be stratified by recruitment site (Greater Manchester Mental Health NHS Foundation Trust, Pennine Care NHS Trust, Mersey Care NHS Trust, Coventry & Warwickshire Partnership NHS Trust, Birmingham & Solihull Mental Health NHS Foundation Trust, South London

Greater Manchester Mental Health NHS Foundation Trust

& Maudsley NHS Foundation Trust, & Southern Health NHS Foundation Trust), ethnic background (African, Caribbean or mixed A/C) and therapy partner (family member or FSM).

Within each stratum, participants (service users and relatives/carers) will be individually randomised to CaFI or treatment as usual (TAU) on a ratio of 1:1, using randomly permuting block sizes. Family Support Members will not be randomised. Instead, they will be matched to service users, who are unable to nominate a relative/carer, randomised to the intervention arm.

A web-based randomisation system will be designed using the bespoke KCTU randomisation system. The randomisation system will be created in collaboration with the trial statistician and the CI and maintained by the King's Clinical Trials Unit for the duration of the project. It will be hosted on a dedicated server within KCL.

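### The 171 per arm quoted for a hazard ratio of 0.6 at 90% power belongs to a hazard ratio of 0.54; at 0.6 the planned 404 participants have about 82% power

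*Protocol*

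**What the plan says.** The Sample size section of the Phase 2 protocol sets the effect of interest as a difference in risk: "A reduction in risk of relapse from 40% during follow-up to 24% (i.e. a risk ratio of 0.6").

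It then turns to a survival calculation, "Using Stata's 'power logrank' command with Schoenfeld's formula", and states that "171 participants per arm would be required for 90% power to detect a hazard ration of 0.6".

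Next it allows for therapist clustering, "with an ICC of 0.01 in the intervention arm". The result is given as "With an average cluster size of 11, 198 participants would be required in each arm for 90% power", and the effect is again expressed as two risks: "to detect a difference in relapse of 40% in the control arm and 24% in the intervention arm". The last step is "Inflating for the expected 2% drop out, we require a total sample size of 404".

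Under Data Analysis, the arms are compared by the log-rank test, followed by a Cox model if its assumptions hold.

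**The concern.** The number 0.6 appears first as a risk ratio and then as a hazard ratio. The two are not interchangeable when 40% of controls relapse. For the same pair of relapse risks the hazard ratio lies further from 1 than the risk ratio, so a hazard ratio of 0.6 is a smaller effect than 40% versus 24% and needs more events.

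The research question concerns time to relapse, and the planned model yields a hazard ratio. Readers will set the result against the one hazard ratio in the Phase 2 sample-size text, 0.6 at 90% power. If the design does not have that power, a null result would seem to rule out a hazard ratio of 0.6 with more assurance than the trial can give.

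**Working it through.** **Inputs from the Phase 2 protocol (Sample size; Assignment of interventions).** Control relapse 40%, intervention relapse 24%, power 90%, Schoenfeld's formula, 1:1 allocation, ICC 0.01 in the intervention arm, mean cluster size 11, 2% dropout, total 404. **Assumptions:** two-sided 5% significance (not stated) and proportional hazards.

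**1. Hazard ratio implied by 40% versus 24%.**
HR = ln(1 − 0.24)/ln(1 − 0.40) = ln(0.76)/ln(0.60) = 0.537.

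**2. Reproducing the 171.** Events needed are E = 4(1.96 + 1.2816)²/(ln HR)². At HR 0.537, E = 108.9, rounded up to 109. The mean event probability is (0.40 + 0.24)/2 = 0.32. Then 109/0.32/2 = 170.3, rounded up to **171 per arm**. The match is exact, which also supports the two-sided 5% assumption.

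**3. The same formula at HR 0.6.** The intervention risk is 1 − 0.60^0.6 = 26.4%, a risk ratio of 0.264/0.40 = 0.66. The mean event probability is 0.332. E = 161.1, rounded up to 162. Then 162/0.332/2 = **244 per arm**, or 488 in total (485 if events are left unrounded).

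**4. Can another reading give 171 at HR 0.6?** Each row changes one input from step 3.

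| Change | Per arm |
|---|---|
| Intervention risk held at 24% | 254 |
| Freedman's formula | 255 |
| 2% withdrawal added | 249 |
| One-sided 5% | 199 |
| 80% power | 183 |
| Control relapse 50% | 193 |
| Control relapse 60% | 159 |
| Control relapse 70% (the figure in the Phase 1 text) | 134 |

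None gives 171. That would need a mean event probability of 162/342 = 0.474, which means control relapse of roughly 55–57% against the stated 40%.

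**5. Power at HR 0.6.** Power = Φ(√E × |ln 0.6|/2 − 1.96), with E divided by the design effect where clustering is allowed for. The design effect in the intervention arm is 1 + (11 − 1) × 0.01 = 1.10, averaging 1.05 over the two arms.

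| Participants | Events | Design effect | Power at HR 0.6 |
|---|---|---|---|
| 342 (171 per arm) | 113.5 | 1 | 77.7% |
| 396 (404 less 2%) | 131.5 | 1 | 83.4% |
| 396 | 131.5 | 1.05 | 81.5% |
| 404 | 134.1 | 1 | 84.1% |
| 404 | 134.1 | 1.05 | 82.3% |

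Using a mean event probability of 0.32 in place of 0.332, with 396 participants and design effect 1.05, gives 80.1%. The range over these choices is 80–84%.

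**6. The 198 and the 404.** Two proportions, 40% versus 24%, with continuity correction give 189 per arm; 189 × 1.05 = 198.5, in line with 198. Then 396 × 1.02 = 403.9, or 404. (Dividing by 0.98 gives 405, an immaterial difference.) Log-rank power at 40% versus 24% with design effect 1.05 is 92.7% at 396 and 93.2% at 404.

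**7. Size needed for 90% power at HR 0.6.** 244 × 1.05 gives 257 per arm; allowing for 2% dropout, about 524 in total.

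**The case against.** The strongest reply is that the final sample size does not depend on the faulty sentence. The 171 is a first step. The 198 and 404 are recalculated for 40% versus 24% and are sound for that effect. The protocol never says outright that 404 gives 90% power at a hazard ratio of 0.6, and the exact match at 171 suggests the right survival proportions were used and only the printed hazard ratio is wrong. No sentence in the Phase 2 text explicitly equates the two ratios. The Cox model is conditional on its assumptions. The 82% also depends on 40% control relapse, and higher relapse would raise it.

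Much of this stands. The trial is not underpowered for its stated risk difference, the total need not change, and the 82% is conditional. But the sentence giving 171 is still false on the protocol's own method and inputs. The text also presents 198 and 404 as the same calculation redone for clustering at the same 90% power, so a reader will naturally credit 404 with 90% power at a hazard ratio of 0.6.

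**Conclusion.** The concern holds. The 171 per arm gives 90% power for a hazard ratio of 0.537 (40% versus 24%); for a hazard ratio of 0.6 it gives 78%. The planned 404 gives about 82% power at 0.6 (80–84% over the clustering, dropout and event-rate choices shown). The chance of missing a true hazard ratio of 0.6 is therefore about 18%, not the 10% a reader would infer. The 404 remains adequate for 40% versus 24%.

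These conclusions rest on a two-sided 5% test, 40% control relapse and proportional hazards.

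**What to change.** Keep 404 and correct the description in the Phase 2 Sample size section, for example:

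> With a two-sided 5% test, 171 participants per arm give 90% power for relapse of 40% versus 24%, equivalent to a hazard ratio of 0.54 under proportional hazards. Allowing for therapist clustering and 2% dropout, the planned 404 give at least 90% power for that effect and about 82% for a hazard ratio of 0.60 (40% versus 26.4%).

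The significance level in this wording is inferred from the match at 171, so the trial team should confirm it. The text should no longer let 0.6 stand for both the risk ratio and the hazard ratio.

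The cost is two sentences and a less favourable power figure at 0.60. Recruitment, endpoint and analysis are unchanged. If 90% power at a hazard ratio of 0.6 is really what is wanted, the total would have to be about 524.

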Quantitative data: Quantitative outcome data will be collected by RAs blind to delivery of the intervention at four-time points: baseline, post intervention (within 1 month) and at 6 and 12-months follow-up. We will ask study participants to complete a self-report socio-demographic questionnaire which is a non-standardised measure. We will collect primary and a variety of secondary outcome data using standardised measures.

Socio-demographic questionnaire

A self-report socio-demographic questionnaire will be used to collect data on key variables such as age, gender, ethnic group and religion will be completed by service users, family members and FSMs. Additional questions for service users will include diagnosis, relationship with the family member/FSM, length of time since first contact with services, inpatient history and medication.

Primary outcome

Time in relapse as rated from service user records (case-notes) defined as a 2-week exacerbation of symptoms leading to a change in management (Barrowclough et al., 1999). This is a Cochrane-recommended measure (Pharoah et al., 2006), which was endorsed as a desired outcome by participants in the CaFI feasibility study as preventing relapse and readmission were significant motivators for engaging in therapy. Past studies (Barrowclough et al., 1999) have demonstrated the ability to predict rating of relapse via case-notes in 98% of cases. We confirmed the feasibility of collecting relapse data in our HS&DR study (Edge et al., 2016).

Secondary outcomes

Other outcomes that were important to our feasibility study participants relate to service use (frequency of admission) and experiences of coercive care, including compulsory detention under the Mental Health Act, length of hospital admission, and use of Community Treatment Orders (CTOs). We shall collect these data from patient records so their collection will not add to the assessment burden. Our previous study also proved the feasibility of collecting the following standardised service user and family secondary outcomes, which will be used in the trial:

Psychosis symptom severity (service users)

The Positive and Negative Syndrome Scale (PANSS) (Kay, Fiszbein, & Opler, 1987) is a widely used 30-item semi-structured interview designed to assess positive, negative and general symptoms in

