Service use data will be collected from patient records (hospital inpatient, outpatient and accident & emergency services) and from a Service-Use Interview (SUI) with participants and family at baseline and at each follow up assessment. The SUI will include questions about whether the participant has used any primary, secondary or community-based health and social care and how often they used the service in the last 3 months (baseline study visit) or since the last assessment (follow-up study visits).

The SUI will ask participants to record whether they have used any hospital inpatient, outpatient or emergency services and the name of the hospital, to facilitate the review of patient records.

The SUI will also include time spent by family as informal carers, use of other public services (e.g. criminal justice system) and time in paid and unpaid employment/productive activity. These data will be used to estimate costs for a broader societal perspective for sensitivity analysis.

Timetable (months) and participant timeline

Total duration: 42 months

1-22 months: Recruiting people to test CaFI and making sure CaFI is acceptable to both Sub Saharan Africa and Caribbean descent

1-40 months:

- Recruiting more people to test CaFI and delivering CaFI to family units
- Collecting information before receiving CaFI
- Collecting information directly after receiving CaFI
- Collecting information 6 months after receiving CaFI
- Collecting information 12 months after receiving CaFI
- Analysing the collect information

31-42 months: share findings with the public (including service users and families), health professionals, policy makers and academics

Participant timeline

Participant recruitment: 22

Duration of intervention/participant: 10 weeks within 20-week therapy window

Duration of follow-up: 12

Trial duration/participant: 17 (including follow-up)

Table 1. Schedule of participant enrolment, interventions and assessments in the CaFI study.

	STUDY PERIOD					
	Enrolment	Allocation	Post-allocation			Close- out
TIMEPOINT**	-t1 Baseline	t ₁	t2 Post- interve ntion	t ₃ 6- month follow-up	t4 12-month	t _x

The University of Manchester			people v	vith psychos	es		NHS Found
ENROLMENT:							
Eligibility screen	X						
Informed consent	X						
Randomisation		X					
INTERVENTIONS:							
Culturally-adapted							
Family Intervention		+					
Treatment as Usual		-					
ASSESSMENTS:							
Relapse data (health records)	X			X	X	X	

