Understanding why effective interventions such as CaFI are successfully implemented in some settings but not others is a key issue for wider uptake and spread. Process evaluation is an essential part of designing and testing a complex intervention and is required to understand how and under what conditions implementation is effective (Moore et al., 2015). There are a large number of theoretical frameworks available to understand the implementation processes (Nilsen, 2015). We will draw upon a theoretical approach known as Normalisation Process Theory (NPT) which facilitates understanding of the extent to which new processes become part of routine practice (May & Finch, 2009). NPT is comprised of four main constructs that represent individual and collective levels of work involved in the implementation of new practice namely, coherence, cognitive participation collective action and reflexive monitoring.

We will conduct semi-structured interviews with around 30 staff (therapists, care coordinators, NHS senior leaders and service managers, commissioners) purposively sampled across all sites. Interview schedules will be informed by NPT and will focus on understanding:

- Sense making: how CaFI is understood and compared with existing practices
- Implementation: how CaFI is developed and translated into practice
- Embedding: how CaFI becomes or does not become routinely incorporated into the everyday work of professionals
- Integration: how CaFI is sustained as part of normal practice

Data Analysis

Statistical analyses will be performed on an intention-to-treat basis. The log-rank test will be used to compare the survival distributions of the two arms. If its assumptions are met, Cox's proportional hazards model will be fitted, allowing adjustment for covariates. All analyses will be appropriately adjusted for therapist clustering.

Qualitative data will be will be digitally-recorded, transcribed verbatim, and analysis will occur blind to trial outcomes to avoid biased interpretation of the findings. Anonymised transcripts will be analysed using Framework Analysis, allowing for both inductive and deductive coding. Deductive coding will be informed by NPT.

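### The stated comparison of the arms is an unadjusted log-rank test, although relapse and admission history is already taken at baseline; adjusting for it would gain a little power at almost no cost

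*Protocol*

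**What the plan says.** Data Analysis (Phase 2 protocol) names the comparison: "The log-rank test will be used to compare the survival distributions of the two arms". It gives no strata and no covariates for that test. It then adds: "If its assumptions are met, Cox's proportional hazards model will be fitted, allowing adjustment for covariates". The covariates are not named. A third sentence applies to everything: "All analyses will be appropriately adjusted for therapist clustering".

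Sample size starts from a log-rank calculation, which fits a reading of the log-rank test as the main comparison.

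On baseline data:
- Table 1 (schedule of assessments) marks relapse data, psychiatric and compulsory admissions, and length of inpatient stays at baseline, all from health records.
- The socio-demographic questionnaire for service users adds "length of time since first contact with services, inpatient history and medication".

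Study design enrols people "in inpatient, rehabilitation, community and forensic settings". Setting appears in the design and eligibility text but is not listed as a baseline variable.

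Under Assignment of interventions, "Randomisation will be stratified by recruitment site", ethnic background and therapy partner.

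**The concern.** In a time-to-event comparison, leaving out a baseline factor that predicts the event pulls the marginal hazard ratio towards 1 and costs some power. Recent relapse and admission history plausibly predicts a further relapse rated from case notes. A person's care setting may do so too, since it affects both underlying risk and how often a change in management is recorded.

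The trial already reads the records that hold the history. An unadjusted log-rank test discards that information. The protocol also makes adjustment depend on an assumption check and puts it after the log-rank test, so a later plan that made the adjusted model primary would depart from the stated order. The economic analysis is handled differently: the protocol commits to adjusting all of those analyses for key covariates, to be identified before the follow-up data are analysed. The clinical comparison has no such commitment.

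At stake is a modest amount of power, and a main result that does not allow for chance imbalance in history or setting.

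**Working it through.** **1. The plan's own figures.** The protocol states 90% power, 40% control relapse and 24% with CaFI. It does not state alpha; two-sided 0.05 is assumed.
- Implied hazard ratio: ln(0.76)/ln(0.60) = 0.537.
- Schoenfeld events: 4 × (1.96 + 1.2816)² / (ln 0.537)² ≈ 109. The mean event probability is (0.40 + 0.24)/2 = 0.32, so 109/0.32/2 = 170.3, rounded up to the stated 171 per arm.
- Two proportions with continuity correction gives 189 per arm. The average design effect, with 1 + (11 − 1) × 0.01 = 1.10 in one arm only, is 1.05. 189 × 1.05 = 198.45, matching the stated 198.
- 396/0.98 = 404.1, matching 404.

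**2. Starting power with 396 analysed.**
- At 40% v 24%: 396 × 0.32 = 126.7 events, power 93.8%.
- At a true hazard ratio of 0.6: intervention risk is 1 − 0.6^0.6 = 26.4%, giving about 131 events and power 83.4% (81.5% after dividing events by 1.05).

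The gap between 83% and 90% arises because 171 per arm corresponds to 0.537, not 0.6. Covariates do not cause it.

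**3. What adjustment adds.** The prognostic hazard ratios and patient mix below are assumptions; the documents give none. All runs use 198 per arm, exponential times and 40% control relapse, without therapist clustering.

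*(a) History and setting, over the range used for the conclusion.* Assumed: 40% with prior relapse, 20% rehabilitation or forensic; 3,000 trials per row; Cox Wald tests. Treatment effect set to give 26.4% or 24% relapse with CaFI.

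| Relapse with CaFI | HR history / setting | Unadjusted | + history | + history and setting |
|---|---|---|---|---|
| 26.4% | 1.5 / 0.7 | 82.4% | 82.4% | 82.6% |
| 26.4% | 2 / 0.5 | 82.3% | 84.3% | 84.9% |
| 26.4% | 3 / 0.3 | 83.5% | 87.9% | 90.2% |
| 24% | 1.5 / 0.7 | 93.6% | 94.1% | 94.4% |
| 24% | 2 / 0.5 | 93.1% | 93.9% | 94.1% |
| 24% | 3 / 0.3 | 92.7% | 94.9% | 96.2% |

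The Monte Carlo standard error of a power near 83% is √(0.83 × 0.17/3000) ≈ 0.7 points, so the ends of the range are approximate.

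*(b) Adding an acute group.* Assumed: 15% acute with HR 1.3 to 1.8, history 2.0 to 3.0, rehabilitation or forensic 0.6 to 0.3; 2,500 trials each. Unadjusted v adjusted power:
- At a marginal HR of about 0.6: 83.8/87.0, 82.5/87.0 and 83.3/90.1, gains of 3.2, 4.5 and 6.8 points.
- At 24%: 94.3/95.2, 93.6/95.7 and 93.2/97.2, gains of 0.9, 2.1 and 4.0 points.

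*(c) Two generic binary predictors, conditional treatment HR 0.6.* Loss from the unadjusted log-rank test against one stratified by both:
- 1.5 × 1.5: about 1 point
- 2 × 2: 2.6 to 3.1
- 2.5 × 2: 3.8 to 5.0
- 2 × 3: 5.5 to 6.9
- 3 × 3: 8.7
- One predictor only, at 1.5 to 2: 0.1 to 1.5

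The adjusted Cox model was within 1 point of the stratified log-rank test throughout.

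**4. Chance imbalance.** The SD of the between-arm difference is √(2 × 0.2 × 0.8/198) = 4.0 points for a factor with 20% prevalence and √(2 × 0.4 × 0.6/198) = 4.9 points for one with 40%. This is ordinary variation under randomisation.

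**The case against.** The strongest objection is that Data Analysis already provides for a covariate-adjusted Cox model, and that the list of covariates belongs in the statistical analysis plan, which is not shown. This stands for the list, and nothing in the protocol says outright that the log-rank test alone decides the trial. It does not answer the point about order: the protocol itself names the unadjusted test as the comparison and makes adjustment conditional. The power loss applies if that test decides.

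At the effect the trial was sized for, 40% v 24%, unadjusted power without clustering stays above 90% in sets (a) and (b). That also stands, and it is why the point concerns efficiency and not validity.

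A reader might infer four stronger things that the documents do not support:
- **That history and setting are the strongest relapse predictors the trial records.** The protocol never ranks predictors or gives their strength, and setting is not a listed baseline item.
- **That a fixed amount of power is given away.** Losses of 7 to 9 points arise only with strong assumed predictors; weak ones give almost nothing.
- **That a log-rank test cannot use baseline values.** A stratified one can.
- **That the randomisation is at fault.** There are already 7 × 3 × 2 = 42 cells, about 10 participants each. Adding three settings and a two-level history would make 252, about 1.6 each.

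**Conclusion.** The point holds as a modest, inexpensive improvement. The protocol makes an unadjusted log-rank test its stated comparison while plausibly prognostic history is already collected at baseline.

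Under assumed hazard ratios of 1.5 to 3 for history and 0.7 to 0.3 for a rehabilitation or forensic setting, adjustment gains about 1 to 6 points of power at a treatment hazard ratio of 0.6 and about 1 to 4 points at 40% v 24%. The gain shrinks towards nil at the weak end and is smaller with history alone. The figures depend wholly on those assumptions and on the assumed patient mix, and they leave out therapist clustering. Type I error is unaffected, and the trial remains valid if nothing is changed.

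**What to change.** In Data Analysis:
- Make the main treatment test and estimate a Cox model adjusted for baseline relapse or admission history from health records, defined over one fixed look-back period. Add care setting at randomisation if it is coded as a baseline field.
- State the fallback in advance: if hazards are non-proportional, use a log-rank test stratified by the same factor.
- Keep the planned adjustment for therapist clustering in whichever analysis is used.
- Report the unadjusted log-rank test and hazard ratio alongside as supportive.
- Leave the randomisation strata unchanged.

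The cost is a short change of text, a stated look-back period and, if setting is used, one coded field. No extra participants or visits are needed, because the records are already read at baseline. The change should be made before outcome data are seen, so that the covariates cannot look data-driven. The drawback is that the adjusted hazard ratio is conditional on the covariates and differs in meaning from the marginal one, which is why both should be reported.
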